**This document is confidential.**

A summary table of incidence of gout flares during TPs 4-6 will be presented, based on the ITT population, but including only patients who were still being followed up at the start of TP 4. The incidence is defined as the total number of gout flares a patient experiences between TP4 day 0 and TP6 day 28, divided by the length of observation of the patient in this time period.

An ANCOVA model will be performed with incidence of gout flares as the dependent variable, and treatment and randomization stratum as fixed effect variables. The LSMean difference between each SEL-212 and placebo treatment group will be provided along with its 95% confidence interval, and 2-sided p-values.

- Gout flare incidence based on self-reported weekly gout flare diary:

A summary table of the incidence of gout flares during the double-blind treatment phase (TP1 to TP6) and during the first 3 months and the next 3 months after start of study treatment based on weekly gout flare diary will be provided by treatment group on the ITT population. The incidence is defined as the total number of gout flares a patients experiences in respective time period divided by the length of observation of the patient in this time period. Additionally a summary table of the total number of gout flares during the double-blind treatment phase (TP1 to TP6) and of the total number of gout flares during the first 3 months and the next 3 months after start of study treatment will be provided by treatment group and severity on the ITT population.

An ANCOVA model will be performed with incidence of gout flares as dependent variable and treatment and randomization stratum as fixed effect variables for the whole treatment period (TP1 to 6) and for the first 3 months (TP1 to 3) on the ITT. The LSMean difference between each SEL-212 and placebo treatment group will be provided along with its 95% confidence interval, and 2-sided p-values.

Additionally, a MMRM will be applied on the ITT with the dependent variable 'incidence of gout flares in the study (TP1-6)' and treatment, 3-month period (months 1-3 versus months 4-6), treatment-by-3-month period interaction, randomization stratum and baseline value of number of gout flares as fixed effects. The LSMean difference between each SEL-212 and placebo treatment group will be presented for each 3-month period, along with its 95% confidence interval, and 2-sided p-values.

- Association between multiomic markers of gout and treatment effect in patients treated with SEL-212:

The treatment effect at TP6, i.e., the number and percentage of patients with responses as defined for the primary efficacy variable (i.e. having sUA value < 6 mg/dL in more than 80% of the time in TP6) will be summarized for each class of multiomic markers by SEL-212 treatment group.

- Immune tolerance related multiomic markers in patients on SEL-212 who developed anti-uricase vs. those patients on SEL-212 that did not develop anti-uricase antibodies, and in patients on SEL-212 who developed anti-pegadricase antibodies vs. those patients on SEL-212 that did not develop anti-pegadricase antibodies:

Summaries for each SEL-212 treatment group will be provided by period and by antibody status.

This document is confidential.

### **9.3.5. Exploratory Endpoints for the Extension Phase**

All endpoints for the extension phase will be summarized descriptively on the ITT population continuing into the extension phase which corresponds to the EPS. Continuous summaries will include the change from baseline (Day 0 of TP1) and additionally the change from baseline of the extension phase D 0 of TP7.

- The change from Baseline to each TP (1 to 12) during the treatment phase of sUA level for EPS:  
Summary table of actual values and change from baseline (i.e., D0 TP1 and also D28 TP6) for mean sUA level will be provided for each TP during the study by treatment group on EPS. Additionally, the percent change in mean sUA from baseline (i.e., D0 TP1 and also D28 TP6) for each TP in the extension phase will be presented by treatment group. 95% confidence intervals will be provided for all mean changes from baseline.
- The change from Baseline to each TP (1 to 12) in number of tender joints and number of swollen joints for EPS:  
A summary table with the number of tender and of swollen joints at scheduled visits and the change from baseline (i.e., D0 TP1 and also D0 TP7) will be provided by treatment group on EPS. 95% confidence intervals will be provided for all mean changes from baseline.
- In patients with tophi at baseline within EPS, the incidence of tophus reduction (i.e., percentage of patients with at least PR in overall tophus response) in each TP (1 to 12):  
Frequency table of number and percentage of tophaceous patients at baseline with / without tophus reduction will be provided by visit and treatment group on the EPS population. Additionally for tophaceous patients at baseline of the extension phase (D0 TP7) a frequency table of number and percentage with / without tophus reduction during the extension phase (TP7 to TP12) will be provided by scheduled visit in extension phase and treatment group.
- The change from Baseline to each TP (1 to 12) in the total score and in subscales of the Health Assessment Questionnaire (HAQ-DI) for EPS:  
A summary table of actual values and change from baseline of the study and of the extension phase (i.e., D0 TP1 and also D0 TP7) of the total score and of subscale scores of HAQ-DI will be provided for each assessment during the study by treatment group on the EPS. 95% confidence intervals will be provided for the mean changes from baseline.
- The change from Baseline to each TP (1 to 12) in the summary score and in subscales of the Short Form Health Survey (SF-36) for EPS:  
A summary table of actual values and change from baseline of the study and of the extension phase (i.e., D0 TP1 and also D0 TP7) of the summary score and of subscale scores of SF-36 will be provided for each assessment during the study by treatment group on EPS. 95% confidence intervals will be provided for the mean changes from baseline.
- Gout flare incidence and percentage of patients with gout flare in extension phase:  
A summary table of the incidence of gout flares during 12 months of treatment duration, and during the first 9, 6 and 3 months after start of study treatment will be provided by treatment group on the EPS. The incidence is defined as the total number of gout flares a patients experiences in respective time period divided by the length of observation of the patient in this time period.

This document is confidential.

Additionally a summary table of the total number of gout flares during 12 months of treatment duration, and during the first 9, 6, and 3 months will be provided by treatment group and severity on the EPS.

Frequency table of the number and percentage of patients reporting at least one gout flare in 12 months of treatment, and in the first 9, 6 and 3 months will be summarized by treatment group on the EPS. Additionally, a frequency table of the number and percentage of patients reporting at least one gout flare in 12 months of treatment, and in the first 9, 6 and 3 months stratified by severity (life-threatening / severe / moderate /mild) and treatment group will be provided on the EPS. The number and percentage of patients with at least one life-threatening or severe versus the number and percentage of patients with only mild or moderate gout flares in 12, 9, 6, and 3 months of treatment will be presented for each treatment group on EPS.

- Percentage of patients with pre-dose sUA values < 6 mg/dL during TPs 1-12 on EPS:  
A frequency table of number and percentage of patients with pre-dose sUA values < 6 mg/dL at each TP during the study will be provided by treatment group on the EPS
- Pre-treatment anti-pegadricase and anti-uricase antibody formation and levels for each treatment period during extension phase in the SEL-212 active treatment arms:  
Summary table of each variable will be provided by treatment period in the extension phase and by SEL-212 treatment group on the EPS. Percentage of patients with development of new tophi in each TP (1 to 12) in the subgroups of tophaceous patients and in non tophaceous patients at baseline of the study on EPS:  
A frequency table of number and percentage of patients who developed new tophi during the whole study from TP1 to TP12 stratified by tophi at baseline (yes/no) will be provided by treatment group on the EPS.
- Change from baseline to each TP (1 to 12) during the study in Provider Global Assessment of Disease Activity for EPS:  
A summary table of actual values and change from baseline of the study and of the extension phase (i.e., D0 TP1 and also D0 TP7) of the Provider Global Assessment of Disease Activity will be provided for each assessment during the study by treatment group on the EPS. 95% confidence intervals will be provided for all mean changes from baseline.
- Length of time patients are anti-uricase antibody free or before induction of anti-uricase antibody levels above baseline in patients receiving SEL-212 during extension phase:  
A summary table by assessment time will be provided for each SEL-212 treatment group on the EPS.
- Length of time patients are anti-pegadricase antibody free or before induction of anti-pegadricase antibody levels above baseline in patients receiving SEL-212 during extension phase:  
A summary table by assessment time will be provided for each SEL-212 treatment group on the EPS.
- Levels of uricase activity in patients receiving SEL-212 for the EPS:  
Summaries for each SEL-212 treatment group will be provided by period TP1 to TP12 on the EPS.

This document is confidential.

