11.2 Gout Assessment

11.2.1 Tophus Assessment

Assessment of tophi will be performed according to the schedule described in [Appendix A](#) and [Appendix C](#).

Baseline photographs of the hands and feet of each patient will be obtained using a standardized method in all patients (whether or not a prevalent tophus was identified by the Investigator at Baseline), together with photographs of up to two other representative sites of tophaceous disease. The baseline photographs will be assessed by a Central Reader to prospectively identify sites of tophaceous disease present at the start of treatment. The Central Reader will be blinded to patient treatment assignment and to the Investigator's identification (or lack of identification) of a tophus to control for potential bias. Up to five tophi in the photographs will be chosen by the Central Reader for measurement over the course of therapy. The Central Reader will assess the photographs for size of each target tophus using the image analysis software. To be considered measurable, tophi are required to be ≥ 5 mm in the longest dimension at Baseline and to have borders distinguishable to the Central Reader. Up to two tophi (approximately > 10 mm in the longest dimension at Baseline) representative of the patient's tophus burden but unable to be accurately measured (e.g., due to location, shape, or other factors), may also be evaluated at the Central Reader's discretion. Once the Central Reader completes the assessment of photographs from a patient's study visit, the Central Reader will not be permitted to change the evaluation.

Individual response for measurable and unmeasured tophi will be assessed by the Central Reader by comparing the tophus area (approximated for unmeasured) to its baseline measurement using assessment categories described in [Table 2](#).

Table 2: Individual Tophus Assessment Categories (by Central Reader)

Assessment	Measurable Tophus	Unmeasured Tophus
Complete Response (CR)	A 100% decrease in the area of the tophus	The disappearance of the tophus
Marked Response (MR)	At least a 75% decrease in the area of the tophus	
Improved (I)		An approximate 50% or more reduction from baseline in the size of the tophus
Partial Response (PR)	At least a 50% decrease in the area of the tophus	
Stable Disease (SD)	Neither a 50% decrease nor a 25% increase in the area of the tophus can be demonstrated	Neither improvement nor progression from baseline can be determined.

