**Statistical Analysis Plan**

Sponsor: Selecta Biosciences

Protocol No.: SEL-212/301

- The change from Baseline to each Treatment Period (7 to 12) in extension phase in number of tender joints and number of swollen joints
- In patients with tophi at Baseline, the percentage of patients with at least PR (as best response) in overall tophus response evaluation in each Treatment Period (7 to 12) in the extension phase
- The change from Baseline to each Treatment Period (7 to 12) in extension phase in the total score and in subscales of the Health Assessment Questionnaire (HAQ-DI)
- The change from Baseline to each TP (7 to 12) in extension phase in the summary score and in subscales of the Short Form Health Survey (SF-36)
- Gout flare incidence in the Treatment Periods 1 to 9 and in the Treatment Periods 1 to 12 and percentage of patients with at least one gout flare in the Treatment Periods 1 to 9 and in the Treatment Periods 1 to 12 in extension phase in the subgroup of patients continued into extension phase
- Number of pre-dose sUA values < 6 mg/dL for each patient stratified by cumulative number of treatment periods 7 to 12 for the subgroup of patients continued into extension phase
- Pre-treatment anti-pegadricase and anti-uricase antibody formation and levels for each treatment period during extension phase in the SEL-212 active treatment arms
- Percentage of patients with development of new tophi in each Treatment Period (7 to 12) in extension phase in the subgroups of tophaceous patients and in non tophaceous patients at study baseline (Day 0 TP1) and at baseline of extension phase (Day 0 TP7)
- Change from baseline to each Treatment Period (7 to 12) in extension phase in Provider Global Assessment of Disease Activity
- Length of time patients are anti-uricase antibody free or before induction of anti-uricase antibody levels above baseline in patients receiving SEL-212 in the subgroup of patients continued into extension phase
- Length of time patients are anti-pegadricase antibody free or before induction of anti-pegadricase antibody levels above baseline in patients receiving SEL-212 during extension phase
- Levels of uricase activity in patients receiving SEL-212 during extension phase
- Levels of monosodium urate crystal deposits and/or total body monosodium urate crystal deposits (imaging patients only) during extension phase
- Levels of inflammatory and tolerogenic biomarkers during extension phase

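### SAP 9.3.5 does not produce the extension-phase new-tophi endpoint, and it leaves the reference for tophus reduction during the extension unstated

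*SAP*

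**What the plan says.** **New tophi.** SAP 4.4 lists the endpoint as "Percentage of patients with development of new tophi in each Treatment Period (7 to 12) in extension phase", split by whether the patient had tophi at study baseline (D0 TP1) and at the baseline of the extension (D0 TP7). Protocol 6.2.4 lists the same endpoint. The analysis text in SAP 9.3.5 describes a single table of "patients who developed new tophi during the whole study from TP1 to TP12 stratified by tophi at baseline (yes/no". The heading above that text refers to each treatment period from 1 to 12, and only to baseline of the study. SAP 12, which records departures from the protocol, mentions only the move from ANCOVA to ANOVA for gout flares.

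**Tophus reduction.** SAP 9.3.5 glosses the quantity as "the incidence of tophus reduction (i.e., percentage of patients with at least PR in overall tophus response". It first gives a by-visit table for patients with tophi at study baseline. It then adds, for patients tophaceous at D0 TP7, that a "frequency table of number and percentage with / without tophus reduction during the extension phase (TP7 to TP12) will be provided by scheduled visit". No reference assessment is named for this second table. The general rule at the top of the section reads "Continuous summaries will include the change from baseline (Day 0 of TP1) and additionally the change from baseline of the extension phase", so it covers continuous variables and is silent on categories such as PR.

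**Response criteria.** Protocol 11.2.1 has the Central Reader classify each tophus by "comparing the tophus area (approximated for unmeasured) to its baseline measurement", using photographs taken at the start of treatment. SAP 6.2.4 likewise ties tophus reduction to baseline for the TP6 endpoint. SAP 7.2 defines a baseline of the extension period at D0 TP7. It takes tophus status at study baseline from the IRT system and names no source for status at D0 TP7.

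**The concern.** An extension-phase endpoint should show what happened in the extension. The new-tophi table runs from the first dose, so new tophi from the first six months enter the extension result, and one of the two defined subgroupings has no table. A programmer following SAP 9.3.5 would not produce the endpoint that SAP 4.4 and the protocol define.

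The reduction table has a different problem: its label promises change during TP7-12, but the only PR definition available looks back to study baseline. Applied literally, it could report a response reached by TP6 as an extension result, or hide regrowth after TP6. Regrowth is a live possibility, because patients who met the stopping rule keep attending extension visits without study drug (Protocol 7.1.4).

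**Working it through.** The plan states no figure on this point, so there is none to reproduce. The check compares definitions and then applies the protocol's thresholds to assumed values.

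**1. New tophi: endpoint against planned table**

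| | SAP 4.4 and Protocol 6.2.4 | SAP 9.3.5 table |
|---|---|---|
| Window | Each of TP7-12 | TP1 to TP12 as a whole |
| Tophus status used | D0 TP1 and D0 TP7 | Study baseline only |
| Declared in SAP 12 | not applicable | No |

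The preamble to SAP section 4 also says that most extension summaries use TP7-12 in place of TP1-6. Protocol 13 requires modifications of planned analyses to be identified in the final SAP.

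**2. What a cumulative count loses**

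Let q6 be the proportion of patients with a new tophus in TP1-6, and q12 the proportion with one in TP7-12 among those free of new tophi until then. The TP1-12 table shows 1 - (1 - q6)(1 - q12). All rates below are assumed.

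| q6 | q12 | TP1-12 table |
|---|---|---|
| 10% | 0% | 1 - 0.90 x 1.00 = 10% |
| 0% | 10% | 1 - 1.00 x 0.90 = 10% |
| 5% | 5% | 1 - 0.95 x 0.95 = 9.75% |
| 20% | 5% | 1 - 0.80 x 0.95 = 24% |

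The first three rows look almost alike but describe quite different extensions. In the fourth, most of the figure predates D0 TP7.

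**3. Reduction: the same tophus under two references**

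Thresholds for a measurable tophus (Protocol Table 2): PR is an area decrease of at least 50%, marked response (MR) at least 75%, progressive disease (PD) an increase of at least 25%, and stable disease (SD) anything between PR and PD. Change = (TP12 area - reference area) / reference area. Areas are assumed, with one measurable tophus per patient.

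| Area at study baseline / D0 TP7 / TP12 | Against study baseline | Against D0 TP7 |
|---|---|---|
| 100 / 45 / 45 | (45 - 100)/100 = -55%: PR | (45 - 45)/45 = 0%: SD |
| 100 / 20 / 26 | (26 - 100)/100 = -74%: PR | (26 - 20)/20 = +30%: PD |
| 100 / 110 / 52 | (52 - 100)/100 = -48%: SD | (52 - 110)/110 = -52.7%: PR |

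The choice of reference therefore changes the category in both directions.

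**4. A patient the criteria do not fit**

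A patient whose first tophus appears in TP1-6 is tophaceous at D0 TP7 and so enters the denominator. That tophus has no study-baseline measurement, and Protocol Table 3 assigns PD for any tophus that appears during the study. The plan does not say how this patient's extension response is classified.

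**The case against.** The best defence concerns the reduction table. The quoted sentence does not say that reduction is judged against study baseline. It selects patients by status at D0 TP7, speaks of the extension phase, and follows a table that already covers study-baseline patients, so a D0 TP7 reference may well have been intended. This stands. The supportable finding is that the reference is missing and that study baseline is the only one defined for PR. A reader might also infer that this table contradicts its endpoint. It does not: the tophus-response endpoint in SAP 4.4 concerns patients with tophi at Baseline, and the first table in SAP 9.3.5 matches it.

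On new tophi, one can say that the heading, by naming each treatment period, includes TP7-12. That is fair, but the table text beneath it gives only the whole-study count, and neither restores the D0 TP7 subgroups.

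Three broader inferences fail:

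- **No efficacy summary isolates the extension.** SAP 9.3.5 gives changes from D0 TP7 for joint counts, HAQ-DI, SF-36 and the provider assessment, and from Day 28 of TP6 for sUA.
- **The flare windows are wrong.** They run "during 12 months of treatment duration, and during the first 9, 6 and 3 months after start of study treatment", which includes the TP1-9 and TP1-12 endpoints in SAP 4.4 and Protocol 6.2.4. Total counts over 12 and 6 months are tabulated on the same set, so mean TP7-12 counts follow by subtraction.
- **Overall complete responders have left the D0 TP7 denominator.** Protocol Table 3 needs complete response in only one tophus with no progression, so such patients may still have tophi. A percentage built on their removal would not be reliable.

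**Conclusion.** The new-tophi point is established from the text alone: the table in SAP 9.3.5 has a different window from the defined endpoint, omits the D0 TP7 subgroups, and the change is undeclared. The reduction point is a gap in specification. Its consequences are conditional on study baseline being used, which is what a literal reading of the response criteria gives but not what the SAP states. The rates and areas above are assumptions that show the direction of the problem; they do not estimate its size in this trial.

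Severity is minor. Extension efficacy is exploratory and descriptive (Protocol 13.4 and SAP 9). The primary endpoint, the key secondary tests, the error rate and the sample size are unaffected.

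**What to change.** In SAP 9.3.5:

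1. **New tophi.** Tabulate patients with tophi first seen after D0 TP7, at the scheduled extension tophus visits, by tophus status at D0 TP1 and at D0 TP7, as SAP 4.4 states. Protocol Appendix C does not schedule photography in every treatment period, so the visit is the workable unit. Keep the TP1-12 table as a supplement. If the cumulative table is preferred alone, declare that in SAP 12.
2. **Reduction.** State that the D0 TP7 table classifies measurable tophi by area relative to the TP6 Day 28/TP7 Day 0 photograph. Name the source of tophus status at D0 TP7. Say how unmeasured tophi, and tophi first seen after study baseline, are handled. If this is not wanted, relabel the table as response against study baseline.

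The cost is SAP wording and programming for new tophi and measurable areas, which use photographs and readings already planned. Unmeasured tophi are the exception. Their size is only approximated against baseline, so programming alone cannot change their reference; they need either a stated exclusion from this table or an added comparison by the Central Reader.

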**Statistical Analysis Plan**

Sponsor: Selecta Biosciences

Protocol No.: SEL-212/301

- Effect on monosodium urate crystal deposits and/or total body monosodium urate crystal deposits (imaging patients only) in EPS:  
Frequencies and summaries will be provided by treatment group, and period, if appropriate.
- Development of inflammatory and tolerogenic biomarkers in EPS:  
Frequencies and summaries will be provided by treatment group, and period, if appropriate.
- Changes in antibody production (anti-uricase and anti-pegadricase) in SEL-212 groups in EPS:  
Summaries for each SEL-212 treatment group will be provided by period.
- Association between multiomic markers of gout and treatment effect in subjects treated with SEL-212 during extension phase:  
The mean sUA level in TPs 1 to 12 and the change from baseline (of the study) will be summarized for each class of multiomic markers by SEL-212 treatment group on EPS.
- Immune tolerance related multiomic markers in patients on SEL-212 who developed anti-uricase and anti-pegadricase antibodies vs. those patients on SEL-212 that did not develop anti-uricase and anti-pegadricase antibodies for EPS:  
Summaries for each SEL-212 treatment group will be provided for each assessment during Treatment Period 1 to 12 in the EPS.

This document is confidential.

